5.1.2. Visit Windows

As participants do not always adhere to the protocol visit schedule, visits will be allocated within each phase to an analysis time point based on the time intervals in [Table 2](#).

If a participant has two or more actual visits in a visit window (“time interval” in [Table 2](#)), only one will be selected as the protocol visit according to the following rules:

1. The measurement closest to the target day will be used.
2. If the measurements fall equidistant from the target day, the last measurement in chronological order will be used.
3. If there are two or more measurements on the same day, then the last measurement in chronological order will be used. If the time of the assessment is not available, the highest record/sequence number will be selected.

Only the protocol visits will be included for calculating summary statistics across participants within a time point or for statistical models using longitudinal data. However, listings or figures

of individual participant-level data (including spaghetti plots), or analyses that identify a maximum or minimum value across time points (e.g., maximum ALT value), may include all measurements.

End of treatment (i.e., EOT) and end of study (i.e., EOS) time points will be included in all analysis over time unless stated otherwise.

Special rule for Follow-up Week 48 (FU W48): Note that the time interval for FU W48 is open on the right, $[324, +\infty)$, while the next time interval is $[352, 379]$. Any visit in follow-up days $[324, 351]$ will be assigned to FU W48. If a patient does not have a visit date in that interval but does have visits on or after follow-up day 352, then the earliest such visit will be assigned to FU W48. Any additional visits on or after follow-up day 352 will be assigned to an “Ext” follow-up visit according to [Table 2](#).

Table 2: Visit Windows

a) Screening and Open-Label Phases

Analysis phase	Target day	Analysis time point (Week)	Analysis time point (Label)	Open-label time interval (Days)
Screening	$-\infty$	-1	Screening	<0
Open-Label	1	0	Baseline	Pre-dose: 1
	15	2	Week 2	$[2, 22]$
	29	4	Week 4	$[23, 43]$
	57	8	Week 8	$[44, 71]$
	85	12	Week 12	$[72, 99]$
	113	16	Week 16	$[100, 127]$
	141	20	Week 20	$[128, 155]$
	169	24	Week 24	$[156, 183]$
	197	28	Week 28	$[184, 211]$
	225	32	Week 32	$[212, 239]$
	253	36	Week 36	$[240, 267]$
	281	40	Week 40	$[268, 295]$
	309	44	Week 44	$[296, 323]$
	337	48	Week 48	$[324, 351]$
	last visit in open-label phase	49 ^a	EOT ^a	

^a End of treatment (EOT) visit will be the last post-baseline visit in open-label phase as defined in [Table 1](#).

b) Follow-Up Phase

Analysis phase	Target day	Analysis time point (Week)	Analysis time point (Label)	Follow-up time interval (Days)
Follow-up	15	50	Follow-up Week 2	[1, 22]
	29	52	Follow-up Week 4	[23, 43]
	57	56	Follow-up Week 8	[44, 71]
	85	60	Follow-up Week 12	[72, 99]
	113	64	Follow-up Week 16	[100, 127]
	141	68	Follow-up Week 20	[128, 155]
	169	72	Follow-up Week 24	[156, 183]
	197	76	Follow-up Week 28	[184, 211]
	225	80	Follow-up Week 32	[212, 239]
	253	84	Follow-up Week 36	[240, 267]
	281	88	Follow-up Week 40	[268, 295]
	309	92	Follow-up Week 44	[296, 323]
	337	96	Follow-up Week 48	[324, $+\infty$)
	365	100	Follow-up Week 52 (Ext)	[352, 379]
	393	104	Follow-up Week 56 (Ext)	[380, 407]
	421	108	Follow-up Week 60 (Ext)	[408, 435]
	449	112	Follow-up Week 64 (Ext)	[436, 463]
	477	116	Follow-up Week 68 (Ext)	[464, 491]
	505	120	Follow-up Week 72 (Ext)	[492, $+\infty$)
	last visit in the study	999 ^a	EOS ^a	

^a End of study (EOS) visit (last available data during the follow-up phase) will be the last visit in the study.

Note: The visits labeled with “Ext” are only for participants who completed PegIFN administration and NA treatment during the follow-up phase.

5.1.3. On-Treatment and Off-Treatment Period

The on-treatment period begins with the first drug intake and finishes with the maximum between:

- Last dose of NA + 2 days
- Last dose of PegIFN- α 2a +10 days
- Last dose of JNJ-3989 + 28 days

The off-treatment period starts after the end of on-treatment period and stops if the NA re-treatment starts.

5.1.4. Missing and Partial Dates Imputation Rules

For analysis and reporting purposes, missing or partial dates in adverse event (AE onset date; AE end date), HBV diagnosis and infection dates, concomitant therapies (start date; end date) will be imputed according to the rules in the following subsections. The original, non-imputed, dates will be used only in listings.

5.1.4.1. Adverse Event Onset Date and Resolution Date

Partial AE onset dates will be imputed as follows:

- If the AE onset date is missing the day only, it will be set to:
 - The first day of the month when the AE occurred, if month/year of the AE onset date is different than the month/year of the first administration of study treatment date.
 - The day of the first study treatment administration, if the month/year of the AE onset date is the same as the month/year of the first study treatment administration but the month/year of the AE resolution date is different.
 - The earliest between the day of the first study treatment administration date and day of AE resolution date, if month/year of the AE onset are the same as both the month/year of the first study drug administration and the AE resolution date.
- If the AE onset date is missing both day and month, it will be set to the earliest of:
 - January 1 of the year of onset, as long as this date is on or after the first study drug administration.
 - Month and day of the first study treatment administration, if this date is in the same year of AE onset date.
 - December 31 if the AE onset date year is prior to the year of the first study drug administration.
 - The AE resolution date.
- Completely missing onset dates will not be imputed.

Partial AE resolution dates not marked as ongoing will be imputed as follows:

- If the resolution date of an AE is missing the day only, it will be set to the earliest of the last day of that month or the day of the date of death, if the participant died in that month.
- If the resolution date of an AE is missing both day and month, it will be set to the earliest of December 31 of that year or the day and month of the date of death, if the participant died in that year.
- Completely missing resolution dates will not be imputed.

5.1.4.2. HBV Diagnosis and Infection Dates

If the reported date is partially missing, the following imputation rules will be applied:

- the 15th of the month, if only the day is missing.
- the 30th of June, if only the year is available.
- No imputation if completely missing.

5.1.4.3. Concomitant Medication Dates

In case of partially missing concomitant medication start/end dates, the following imputation rules will be applied:

- the 15th of the month, if only the day is missing.
- the 30th of June, if only the year is available.
- If the imputed start date is after the concomitant medication end date, further adjustment of the imputed start dates is required. It will be imputed as the concomitant medication end date.
- No imputation if completely missing.

If the medication was taken prior to study start based on eCRF question, and the imputed start date is after first treatment date, further adjustment of the imputed start date is required. It will be imputed as the day prior to first dosing date.

If the medication was taken after study start based on eCRF question, and the imputed start date is prior to first dosing date, the imputed start date will be further adjusted to be the first study treatment dosing date. The partially missing medication end date will be imputed following the rule described at the beginning of this section to ensure it is on or after first dosing date, and after its start date.

- In case of a completely missing start date, the concomitant therapy will be considered as having started before the trial, unless the eCRF indicating that the medication was taken after study start.
- In case of a completely missing end date, the concomitant therapy will be considered as ongoing at the end of the trial, unless the eCRF indicating not ongoing.

5.1.5. Data Handling Rules

Those measurements collected from screening visit to the end of study will be handled according to the following rules summarized in [Table 3](#).

Table 3: Data Handling Rules for HBV Virology and Serology Assessments

HBV parameter	LLOQ	ULOQ	Imputed Values	
			If value < LLOQ	If value > ULOQ
HBsAg	0.05 IU/mL	249,750.00 IU/mL with dilution	0.025 IU/mL ^(a)	274,725.00 IU/mL ^(b) with dilution
HBeAg	0.11 IU/mL	7,000.00 IU/mL with dilution	0.055 IU/mL ^(a)	7,700.00 IU/mL ^(b) with dilution
HBcrAg*	3.0 Log ₁₀ U/mL	9.0 Log ₁₀ U/mL with dilution	2.7 Log ₁₀ U/mL	9.9 Log ₁₀ U/mL ^(b) with dilution
HBV DNA	20 IU/mL	170,000,000 IU/mL w/o dilution	If target detected: 15 IU/mL** If target not detected: 5 IU/mL **	187,000,000 ^{(b)(c)} IU/mL w/o dilution
HBV RNA*	LLOQ = 2.939 log ₁₀ cp/mL (i.e., 869 cp/mL) LOD = 1.398 log ₁₀ cp/mL (i.e., 25 cp/mL)	NAP	If < LOD or target not detected then 1.114 log ₁₀ cp/mL (13 cp/mL)	NAP
Anti-HBs	5 mIU/mL	10000.0 mIU/mL	2.5 mIU/mL ^(a)	11000.0 mIU/mL ^(b)

* As new assays become available different data handling rules may apply

** For HBV DNA <LLOQ: Spaghetti plots showing absolute values, the imputed value will be 15 IU/mL for both target detected and target not detected. All other tables, listings and figures, will be produced using 15 IU/mL as an imputed value if target is detected and 5 IU/mL if target is not detected.

Key: NAP=Not applicable

(a) LLOQ/2

(b) ULOQ+(ULOQ/10)

(c) If the original result > ULOQ, then take the re-test value (i.e., diluted result). If the diluted result is not available, use the imputed value of the original result indicated in this table.

All other non-intrahepatic viral activity data not included in the data handling rules above, as well as continuous intrahepatic parameters obtained from liver biopsies (e.g., liver concentration of JNJ-3989), with values <LLOQ will be imputed by the LLOQ divided by 2. For parameters reported on the log scale, imputed values should be derived on the linear scale, not the log scale, and then converted back to the log scale. E.g., if a parameter has LLOQ = 3.0 Log₁₀ U/mL (equivalent to 1,000 U/mL), the imputed value should be log₁₀(10^{LLOQ}/2) = LLOQ - log₁₀(2) = 2.7 Log₁₀ U/mL (equivalent to 500 U/mL).

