5.5. Exploratory Endpoints Analysis

5.5.1. Relationship Between Intrahepatic and Blood Markers

Relationships between intrahepatic and blood markers (Table 4) and/or their change from baseline at Week 40 will be evaluated graphically with scatter plots displaying individual associations.

Means on pooled individual data by study panel and overall mean will also be plotted on the same graph.

The following correlation coefficients will be calculated by study panel and overall for the different correlation scenarios:

- Pearson's correlation coefficient for two continuous variables.
- Phi correlation coefficient for two binary variables.
- Point biserial correlation coefficient for one binary variable and one continuous variable.

Potential relationship on the selected subgroups defined in Section 5.7.4 will also be explored using the same graphical approach.

The following markers will be considered, i.e., each intrahepatic marker will be plotted against each blood marker:

Table 4: List of Intrahepatic and Blood Markers of Interest

Intrahepatic Markers/Endpoints	Blood Markers/Endpoints
• Proportion of HBsAg+ hepatocytes at Week 40	• HBV DNA level at Week 40 (\log_{10})
• Change from Baseline at Week 40 in proportion of HBsAg+ hepatocytes	• HBV RNA level at Week 40 (\log_{10}) • HBsAg level at Week 40 (\log_{10})

 • Proportion of cccDNA-positive hepatocytes at Week 40 • Change from Baseline at Week 40 in proportion of cccDNA-positive hepatocytes • Proportion of pgRNA-positive hepatocytes at Week 40 • Change from Baseline at Week 40 in proportion of pgRNA-positive hepatocytes • pgRNA levels at Week 40 (\log_{10} copies/ cell) • Change from Baseline at Week 40 in pgRNA levels (\log_{10} copies/ cell) • 	
 • HBeAg level at Week 40 (\log_{10}) • HBcrAg level at Week 40 (\log_{10}) • Change from Baseline at Week 40 in HBV DNA (\log_{10}) • Change from Baseline at Week 40 in HBV RNA (\log_{10}) • Change from Baseline at Week 40 in HBsAg (\log_{10}) • Change from Baseline at Week 40 in HBeAg (\log_{10}) • Change from Baseline at Week 40 in HBcrAg (\log_{10}) • Maximum on-treatment ALT decrease • HBsAg seroclearance at FU Week 24
--	---

Additional markers and endpoints may be evaluated when data will be available.

5.5.2. Association Between Baseline Characteristics or Intrahepatic/Blood Markers with Efficacy Variables

The following list of efficacy endpoints of interest will be evaluated:

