5.5.5. HBV RNA and HBcrAg

HBcrAg will be summarized by treatment history (not currently treated and virologically suppressed) and overall, while HBV RNA will only be summarized by treatment history.

The values of and changes from baseline in HBV RNA and HBcrAg, respectively, will be summarized only descriptively over time in a similar manner as for values and changes from baseline over time in HBsAg, HBeAg, and HBV DNA as described in Section 5.4.2.4.1, including the change from baseline value to nadir (i.e., maximum decrease for each participant) and the various graphical displays.

Waterfall plots for changes from baseline of HBV RNA and HBcrAg will also be presented.

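### SAP Table 3 applies the above-ULOQ imputation rule to the log10 number for HBcrAg (9.9, or 7.94 x ULOQ) but to linear units in the other four rows (1.1 x ULOQ); the linear-scale entry would be 9.04

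*SAP*

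**What the plan says.** Table 3 in SAP Section 5.1.5 sets the value to be used when a virology or serology result falls outside the quantifiable range. Five of the above-ULOQ cells carry footnote (b), which defines the imputed value as ULOQ + ULOQ/10 and names no scale. Four of those rows (HBsAg, HBeAg, HBV DNA, anti-HBs) are in linear units. The fifth, HBcrAg, is in log10 units, with a ULOQ of 9.0 log10 U/mL and an imputed value of "9.9 Log ₁₀ U/mL ^(b) with dilution". The HBcrAg row also has an asterisk: "As new assays become available different data handling rules may apply".

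The paragraph under the table says that for log-reported parameters "imputed values should be derived on the linear scale, not the log scale, and then converted back to the log scale". Its worked example takes an LLOQ of 3.0 log10 U/mL to 2.7, which are the LLOQ and below-LLOQ figures printed in the HBcrAg row.

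HBcrAg results are used in two places. In Section 5.5.5, "HBcrAg will be summarized by treatment history (not currently treated and virologically suppressed) and overall", and values and changes "will be summarized only descriptively over time". That section also asks for change to nadir, and "Waterfall plots for changes from baseline of HBV RNA and HBcrAg will also be presented". In Section 5.5.1, Table 4 lists "Change from Baseline at Week 40 in HBcrAg" among the blood markers to be plotted against and correlated with intrahepatic markers, with Pearson's coefficient for pairs of continuous variables.

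**The concern.** One footnote has two meanings. In four rows a result above ULOQ is placed 10% above the limit. In the HBcrAg row it is placed nearly eight times above the limit, because ten per cent of a logarithm is not ten per cent of a concentration.

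HBcrAg is analysed in log10 units, so the extra distance passes straight into change from baseline. Compared with the convention of the other rows:

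- if only the baseline value is above ULOQ, the decline is enlarged;
- if only the later value is above ULOQ, a rise is enlarged;
- if both are above ULOQ, the change is the same under either number.

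The imputed value enters the means, standard deviations, standard errors, 80% confidence intervals and ranges of SAP Section 5.1.6, the waterfall plots and the Pearson correlations. In panels of 8 to 12 participants, one imputed value can be visible.

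**Working it through.** **1. Reproduce the plan's figures.** All inputs are from SAP Table 3. The rule is footnote (b), imputed = ULOQ + ULOQ/10.

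| Row | ULOQ | Imputed | Imputed / ULOQ (linear) | Step in log10 |
|---|---|---|---|---|
| HBsAg | 249,750 IU/mL | 274,725 | 1.100 | 0.041 |
| HBeAg | 7,000 IU/mL | 7,700 | 1.100 | 0.041 |
| HBV DNA | 170,000,000 IU/mL | 187,000,000 | 1.100 | 0.041 |
| Anti-HBs | 10,000 mIU/mL | 11,000 | 1.100 | 0.041 |
| HBcrAg | 9.0 log10 U/mL | 9.9 log10 U/mL | 10^9.9 / 10^9 = 7.943 | 0.900 |

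The HBcrAg figure reproduces only if the footnote is applied to the printed log number: 9.0 + 9.0/10 = 9.9. The addition is right; the scale differs from the other four rows.

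**2. Apply the footnote to HBcrAg on the linear scale.** log10(10^9 + 10^9/10) = log10(1.1 x 10^9) = 9.0414, or 9.04 log10 U/mL.

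**3. Difference.** 9.9 - 9.0414 = 0.8586 log10, and 10^0.8586 = 7.22. Each HBcrAg value above ULOQ is placed 0.86 log10, or 7.2-fold, higher than the other rows' convention gives.

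**4. Which scale does the SAP use for log-reported assays?**

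- The text under Table 3 calls for the linear scale.
- HBV RNA is the only other log-reported row in Table 3. Its limit of detection is 25 cp/mL (1.398 log10) and its imputed value is 13 cp/mL (1.114 log10). Half of 25 is 12.5, which rounds to 13, and log10(13) = 1.114. Halving the log number would have given 0.699. That row is linear.
- The HBcrAg below-LLOQ cell does not settle the matter alone. Linear halving gives log10(1000/2) = 2.699; taking a tenth off the log number gives 3.0 - 0.3 = 2.700. Both print as 2.7, and the cell carries no footnote (a).

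**5. Effect on a group mean.** Each participant above ULOQ at baseline only shifts the mean change by 0.8586/n.

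| n | Group | Shift (log10) |
|---|---|---|
| 8 | Smallest planned panel (SAP Section 3) | 0.107 |
| 12 | Largest planned panel | 0.072 |
| 16 | Treatment-history group: 12 plus all 4 Panel 3 participants (SAP Section 1) | 0.054 |
| 18 | Overall, lower planned total for Panels 1 and 2 | 0.048 |
| 24 | Overall, upper planned total for Panels 1 and 2 | 0.036 |
| 28 | 24 plus 4 from Panel 3 | 0.031 |

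SAP Sections 1.2 and 3 give Panel 3 a target of 4 to 6. With 6, the 16 becomes 18 (0.048) and the 28 becomes 30 (0.8586/30 = 0.029). In a waterfall plot, the affected participant's own bar moves by the full 0.86. With no such participant the shift is 0.

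**The case against.** The best defence is that no rule is broken to the letter. The footnote says ULOQ + ULOQ/10, the ULOQ printed in that row is 9.0, and 9.9 follows. The linear-scale sentence sits in a paragraph that opens with below-LLOQ values of parameters outside the table, so on its terms it does not govern an above-ULOQ cell inside it. The row could even be read as consistent on the log scale, at minus and plus ten per cent. SAP Amendment 1 also records that the HBcrAg cutpoints were revised, so the cell has been looked at since the original SAP. Finally, a value above ULOQ is right-censored, so both 9.9 and 9.04 are placeholders and nothing shows which lies nearer the truth.

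Some of this stands. The formal scope of that paragraph is as described, the HBcrAg row alone does not prove mixed scales, and 9.04 is no better as an estimate of the true concentration. It does not rescue the entry. The SAP states the linear principle for log-reported parameters, illustrates it with this row's own LLOQ figures, and follows it in the HBV RNA row. Neither the asterisk, which concerns future assays, nor the cutpoint revision gives a reason for a different scale. The case for 9.04 is therefore consistency with the SAP's own convention.

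On impact, the objection is largely right. Medians are reported beside means. Protocol Section 1.3.1 (footnote bb) allows only selected HBcrAg samples to be tested. The limit already applies after dilution, so exceedances may be few or none. Change to nadir is a weaker example than the others: Section 5.5.5 still asks for it but refers to Section 5.4.2.4.1, which now covers only change over time.

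**Conclusion.** The HBcrAg above-ULOQ entry is inconsistent with the other four footnote (b) rows and with the SAP's linear-scale convention. It is 0.86 log10 (7.2-fold) higher than that convention gives, 9.9 against 9.04 log10 U/mL. Each participant above ULOQ at baseline only would enlarge the mean HBcrAg decline by 0.07 to 0.11 log10 within a panel of 12 to 8, and by about 0.03 to 0.05 overall.

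This is a minor point. The arithmetic is certain. Any effect on results depends on at least one HBcrAg value exceeding 9.0 log10 U/mL at one of two compared visits, and the documents do not say how often that happens. The primary endpoint does not use HBcrAg. The baseline HBcrAg categories in SAP Table 9 (below 3, 3 to below 4, 4 and above) are unchanged, since both numbers fall in the top category.

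**What to change.** In SAP Table 3, replace 9.9 with 9.04 log10 U/mL, the value of log10(1.1 x 10^9). In footnote (b), add that for assays reported in log10 the rule is applied on the linear scale and the result converted back.

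The cost is one number, one clause and one derivation line. If no HBcrAg result exceeds ULOQ, no output changes. If any does, and HBcrAg was tabulated at an earlier interim analysis with 9.9, the later tables will differ from those outputs and a short note should say why.

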5.1.6. Analysis Specifications

In general, continuous variables will be summarized using descriptive statistics including the number of participants, mean, standard deviation (SD), standard error (SE), 2-sided 80% confidence interval (CI), median, and range. Binary or categorical variables will be summarized using the number and percentage of participants in each category. For time-to-event variables, a summary table including number of participants included in the analysis, number of participants censored, 25th and 75th percentiles and median time-to event will be shown. Graphic displays will also be used to summarize the data.

Descriptive statistics on actual values (original unit and log₁₀ transformed values, when appropriate) and changes from baseline (log₁₀ transformed values when appropriate) will be

summarized over time. Mean (+/- SE) plots of the actual values and the change from baseline (\log_{10} transformed when appropriate) will be presented over time.

As applicable, analyses will be carried out separately for each panel, for the combination of Panels 1 and 2, for the combination of all three panels, and for the pooled cohorts – across all three panels – of participants who are (1) HBeAg positive and not currently treated and (2) HBeAg negative and virologically suppressed by an NA. Additionally, some analyses will be carried out separately for participants who opt out of receiving PegIFN- α 2a and those who opt to receive it for 12 or 24 weeks.

5.1.7. Level of Significance

Due to the exploratory nature of this study, no formal statistical test will be performed. Two-sided 80% CI will be provided with the summary statistics. No adjustment for multiple CIs will be made.

5.2. Participant Dispositions

The number and percentage of participants who are screened, fail screening, and reason for that screening failure will be tabulated by study panel for the Screened Analysis Set.

The number and percentage of participants enrolled, enrolled and not treated, and reason for not being treated will be tabulated by study panel for the Enrolled Analysis Set.

Study disposition and treatment disposition will be summarized for the ITT Analysis Set, as described below.

An overview of the study disposition will be provided by analysis phase, study panel, and overall. The number and percentage of participants who completed or discontinued (or are ongoing [except the final analysis]) and the number and percentage of participants for each study discontinuation reason will be summarized.

An overview of the treatment disposition will be provided. The number and percentage of participants who completed or discontinued study treatment or were ongoing at the time of the IAs or primary analysis cut-off (except the final analysis) will be presented by analysis phase, study panel, and overall. The incidences of treatment discontinuation reasons will also be summarized by analysis phase, study panel, and overall.

A listing including information (i.e., study panel, the date of last study visit, the last analysis phase and time point [phase and week], the date of discontinuation and the reason) on participants who prematurely discontinue from the study and/or study treatment will be included. Information on NA discontinuation and/or re-treatment will also be included.

